3.2.2 Study treatment

The duration of exposure, actual cumulative dose, dose intensity (DI) and relative dose intensity (RDI) will be summarized by treatment group for the safety set.

To assess tolerability, dose delay and dose reduction for the study treatment will be summarized by treatment group. By-patient listings will be provided.

Summary of duration of exposure of study treatment will include categorical summaries (based on clinically meaningful time intervals like < 4 weeks, 4-8 weeks, 8-12 weeks, >=12 weeks etc.) and continuous summaries (i.e. mean, standard deviation etc) using appropriate units of time.

The actual cumulative dose of the study treatment, DI, RDI and RDI categories to measure compliance will be summarized with descriptive statistics by treatment. The predefined

categories for RDI are $< 0.5, \ge 0.5 - < 0.75, \ge 0.75 - < 0.9, \ge 0.9 - < 1.1$ and ≥ 1.1 . The number and proportion of patients within each category will be presented by treatment group.

The number (%) of patients who have dose reductions or interruptions, and the reasons, will be summarized by treatment. Patient level listings of all doses administered on treatment along with dose change reasons will be produced.

3.2.3 Prior and concomitant therapies

Concomitant therapies are defined as any medications (excluding study treatment, prior antineoplastic treatments) and significant non-drug therapies (including physical therapy and blood transfusions) administered in the study and are recorded in the Concomitant Medications/significant non-drug therapies eCRF. These therapies will be coded using the WHO Drug Reference Listing (WHO DRL) dictionary that employs the WHO Anatomical Therapeutic Chemical (WHO ATC) classification system.

Any concomitant therapies starting prior to or after the start of study treatment will be listed.

The imputation of a concomitant medication start date will follow the same conventions as for an AE start date (see Section 3.5.2 Adverse events). No imputation will be performed for concomitant medication end dates.

3.3 Analysis of the primary variable(s)

Phase I: dose-escalation part 3.3.1

The primary objective for the Phase I dose-escalation part of this study is to estimate the MTD and/or RP2D of PDR001 in adult patients with advanced solid tumors. Dose recommendation and estimation of the RP2D/MTD during the dose-escalation part of the study will be supported by the following co-primary variables:

- The AUC_(0-336h) after first dose of treatment in cycle 3 for patients in the DDP.
- The incidence of DLTs in the first cycle of treatment for patients in the DDS.

The corresponding primary analysis for dose-escalation is based on an adaptive Bayesian linear regression of PDR001 exposure and Bayesian logistic regression model (BLRM) guided by the escalation with overdose control (EWOC) principle using the methodology described in detail in [CPDR001X2101 Amendment 8 Section 10.4.2].

All tables and listings will be presented by treatment in which data from different Phase I cohorts treated with the same dose and schedule will be pooled in the CSR.

The final RP2D for future development will be based on considerations of the PDR001 exposure, the BLRM for DLT, and overall clinical assessment of all available safety, tolerability, and PK data from all cycles at all different dose levels tested.

Statistical hypothesis, model, and method of analysis 3.3.1.1

The dose escalation will be guided by both PDR001 exposure and the DLT rate. Details of the guidelines for dose escalation and determination of the RP2D/MTD are provided in [CPDR001X2101 Amendment 8 Section 6.2.3].

3.3.1.1.1 Dose Exposure Bayesian Linear Regression Model

Dose-exposure relationships will be estimated for PDR001 via the following dose-exposure Bayesian linear model, in order to guide the dose recommendation to targeted exposures of PDR001.

$$\log(AUC_i) = \log(\alpha) + \beta \log(d_i/d^*) + \varepsilon_i, \qquad \alpha > 0, \beta > 0$$

where $i=1,\ldots,n$ is the i-th patient in the study, d_i is the dose received by the i-th patient, AUC_i is the area under the curve of PDR001 concentrations for the i-th patient during the interval of 0 to 336 hours after the first dose of treatment in cycle 3. The residual error ϵ_i follows a Normal distribution with mean of 0 and variance σ^2 . Doses are rescaled as d_i/d^* with reference dose $d^*=3$ mg/kg of PDR001. The prior distributions for parameters $log(\alpha)$, $log(\beta)$, and σ are derived based on published summary data of Nivolumab and Pembrolizumab (Robert 2014, Deeks 2014).

From the estimation of the Bayesian linear model, the following posterior summaries will be derived for each dose level of PDR001:

- Mean, median, standard deviation and 95%-credible interval for the exposure of PDR001, as measured by AUC(0-336h) after first dose of treatment in cycle 3.
- The probability that the true $AUC_{(0-336h)}$ after first dose of treatment in cycle 3 achieves the target exposure, as measured by $AUC_{(0-336h)} \ge 1000 \,\mu\text{g*day/ml}$.

Prior specifications

The meta-analytic-predictive (MAP) approach was used to derive an informative prior for $log(\alpha)$, $log(\beta)$, and σ from published AUC data on Nivolumab and Pembrolizumab. For details on the MAP approach see Neuenschwander et al. (2010), Schmidli et al (2014).

The MAP distributions were derived. A normal distribution was used to approximate the MAP distribution for $\log(\sigma)$. For the regression coefficients $(\log(\alpha), \log(\beta))$, a three-component multivariate normal mixture distribution was used to approximate the derived MAP distribution. To allow for more robust inference in case of the discrepancy between MAP information and the trial data, a non-informative prior component was added as the 4th component. The respective distribution for each component and its weight is provided in Table 3-1.

Table 3-1 Prior distribution of (log(Alpha), log(Beta)) and σ for the new trial

Parameter	Means	Standard deviations	Correlation	Weight
Component 1:				
$log(\alpha)$, $log(\beta)$	(6.40, 0.05)	(0.683, 0.180)	-0.463	0.480
Component 2:				
$log(\alpha)$, $log(\beta)$	(6.38, 0.05)	(0.403, 0.118)	-0.773	0.425
Component 3:				
$log(\alpha)$, $log(\beta)$	(6.42, 0.05)	(1.410, 0.257)	-0.217	0.095
Prior for σ:	LN(-0.97, 0.317 ²)			

For further details on the Bayesian linear model including the prior specification for the model parameters along with simulation results that show the operating characteristics of the Bayesian linear model design, refer to [CPDR001X2101 Amendment 8 Appendix 3-Section 14.3.1].

If the dose-exposure does not follow a linear relationship in the natural log scale, non-linear curves will be assessed via data visualization and/or non-linear modeling.

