**Table 14-7 Prior distributions of model hyper-parameters (N=Normal, LN= Log-Normal)**

Parameter	Prior	Median (95% interval)
$\mu_a$	$N(6, 10^2)$	“flat”
$\tau_a$	$LN(-0.693, 0.707^2)$	0.5 (0.125, 2)
$\mu_b$	$N(0, 0.354^2)$	0 (-0.693, 0.693)
$\tau_b$	$LN(-2.079, 0.354^2)$	0.125 (0.063, 0.25)
$\rho$	Uniform(-1, 1)	
$\mu_s$	$N(-1.386, 0.707^2)$	-1.386 (-2.772, 0)
$\tau_s$	$LN(-1.386, 0.707^2)$	0.25 (0.063, 1)

The parameters  $\tau_a$ ,  $\tau_b$  and  $\tau_s$  quantify the degree of between trial heterogeneity on the intercept, log(slope) and error standard deviation of the dose-exposure regression model, respectively. The choices of prior for those parameters reflect the assumption that the exposure at  $d^*$  may vary considerably between the different compounds but the slope may be similar.

2. Published summary data on Nivolumab and Pembrolizumab from three studies are available (see Section 14.3.1.3) and summarized in Table 14-8 after unit conversion is applied on source data.

**Table 14-8 Geometric mean (micro gram day/mL) and geometric CV% of AUC data from three Nivolumab or Pembrolizumab studies**

Dose (mg/kg)	Study 1		Study 2		Study 3	
	N	G. Mean (CV%)	N	G. Mean (CV%)	N	G. Mean (CV%)
1	3	160 (20)			37	92 (34)
2			89	643 (37)		
3	3	975 (24)			42	323 (46.5)
10	8	2282 (31)	83	2770 (33)	52	1526 (59)

The geometric mean and CV% of AUC data can be converted to the sample mean (SM) and sample variance (SV) of log(AUC) through the equations:

$$SM \text{ in log scale} = \log(\text{geometric mean})$$

$$SV \text{ in log scale} = \log(1+(CV\%/100)^2)$$

The distributions of aggregate data were then used to capture the data likelihood as follows:

$$SM_{h,d} \sim N((\log(\alpha_h) + \beta_h \log(d/d^*)), \sigma_h^2/n_{h,d})$$

$$SV_{h,d} \sim \text{Gamma}((n_{h,d}-1)/2, (n_{h,d}-1)/(2\sigma_h^2))$$

where  $n_{h,d}$ ,  $SM_{h,d}$  and  $SV_{h,d}$  are the sample size, sample mean and sample variance of log(AUC) for the dose group  $d$  and trial  $h$ , respectively.

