3. The MAP distributions were derived based on the priors in step 1 and available previous study result summary in step 2. A Normal distribution was used to approximate the MAP distribution for log( $\sigma$ ). For the regression coefficients (log( $\alpha$ ), log( $\beta$ )), a three-component multivariate normal mixture distribution was used to approximate the derived MAP distribution. To allow for more robust inference in case of the discrepancy between MAP information and the trial data, a non-informative prior component was added as the 4th

[figure not shown]
component. The respective distribution for each component and its weight is provided in [Table 14-9](#).

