**Table 14-9 Prior distribution of (log(Alpha), log(Beta)) and sigma for the new trial**

Parameter	Means	Standard deviations	Correlation	Weight
Component 1:				
log( $\alpha$ ), log( $\beta$ )	(6.40, 0.05)	(0.683, 0.180)	-0.463	0.480
Component 2:				
log( $\alpha$ ), log( $\beta$ )	(6.38, 0.05)	(0.403, 0.118)	-0.773	0.425
Component 3:				
log( $\alpha$ ), log( $\beta$ )	(6.42, 0.05)	(1.410, 0.257)	-0.217	0.095
Prior for <math>\sigma</math>:	LN(-0.97, 0.317  )			

[Figure 14-1](#) shows a visualization of the geometric mean AUC at each interested dose level together with a 95% interval, predicted by the priors in [Table 14-9](#).

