## Study 2 (Pembrolizumab, Robert et al 2014)

**Table 14-11 Area under the pembrolizumab concentration versus time curve at steady state by treatment arm**

	2 mg/kg Q3W n=89	10 mg/kg Q3W n=83
Median, g•day/L	0.654	3.76
Geometric mean, g•day/L	0.643	3.77
Geometric CV, %	37	33
5th and 95th percentiles, g•day/L	0.345–1.12	2.13–5.99
Range, g•day/L	0.254–1.27	1.85–7.00

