**Figure 14-2 Visualization of five hypothetical profiles**

**Simulation parameters**

To examine the data sufficiency, four sample set with various sample sizes ranging from 18 to 24 were considered for each dose-exposure profile:

1. 6 patients at each dose level (1 mg/kg, 3mg/kg, and 10 mg/kg); total N = 18
2. 3, 9, 6 patients at 1 mg/kg, 3mg/kg, and 10 mg/kg, respectively; total N = 18
3. 3, 12, 6 patients at 1 mg/kg, 3mg/kg, and 10 mg/kg, respectively; total N = 21
4. 3, 12, 9 patients at 1 mg/kg, 3mg/kg, and 10 mg/kg, respectively; total N = 24

There are total 20 scenarios to be simulated combining 5 dose-exposure profiles and 4 sample set considerations. 500 trials were used to simulate each of the 20 scenarios. For each trial, the AUC data for individual patients were randomly generated from a Log-Normal distribution where

$\log(\text{AUC}) \sim \text{Normal}(\log(\text{mean as specified in Table 14-13}), \text{standard deviation}=0.4)$ .

For each simulated trial, the Bayesian Linear Regression Model was implemented using the simulated AUC data with the priors specified in Section 14.3.1.2.

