## Results

Table 14-14 summarizes the probabilities of the dose recommended from the model for the five different profiles and four sample sets studied. Based on the dose-exposure analysis, a dose is recommended for a trial if this dose meets the following criteria:

- (1) posterior mean exposure at this dose  $\geq 1000 \mu\text{g}\cdot\text{day}/\text{mL}$ , and
- (2) posterior probability of exposure greater than 1000  $\mu\text{g}\cdot\text{day}/\text{mL} > 50\%$ .

**Table 14-14 Summary of recommendation rate for all profiles and sample sets at various doses based on the dose recommendation criteria (1) and (2)**

Profile	Sample Set	Probability (%) that a dose level is recommended							
		0.3 mg/kg	1 mg/kg	2 mg/kg	3 mg/kg	5 mg/kg	7 mg/kg	9 mg/kg	10 mg/kg
1	1	0	0	0	76	100	100	100	100
	2	0	0	0	77	100	100	100	100
	3	0	0	0	79	100	100	100	100
	4	0	0	0	82	100	100	100	100
2	1	0	0	0	0	0	49	99	100
	2	0	0	0	0	0	48	99	100
	3	0	0	0	0	0	48	99	100
	4	0	0	0	0	0	42	99	100
3	1	0	47	100	100	100	100	100	100
	2	0	50	100	100	100	100	100	100
	3	0	51	100	100	100	100	100	100
	4	0	52	100	100	100	100	100	100
4	1	0	0	3	83	100	100	100	100
	2	0	0	1	63	100	100	100	100
	3	0	0	0	70	100	100	100	100
	4	0	0	0	61	100	100	100	100
5	1	0	0	0	81	100	100	100	100
	2	0	0	0	84	100	100	100	100
	3	0	0	0	86	100	100	100	100
	4	0	0	0	87	100	100	100	100

Table 14-15 below summarizes the percentages of the recommended dose of the model for the five different profiles and four sample set studied. Based on the dose-exposure analysis, a dose is recommended for a trial if this dose meets the criteria (1) and (2) and the following added criteria (3):

- (3) Highest posterior probability of exposure lying in the interval of 800 - 1200  $\mu\text{g}\cdot\text{day}/\text{mL}$  among all provisional doses (e.g. 0.3, 1, 2, 3, 5, 7, 9 and 10 mg/kg).

**Table 14-15 Summary of recommendation rate for all profiles and samples set at various doses based on the dose recommendation criteria (1), (2), and (3)**

Profile	Sample Set	Probability (%) that a dose is recommended				
		1 mg/kg	3 mg/kg	10mg/kg	Other doses recommended	No dose recommended
1	1	0	65	0	0	35
	2	0	64	0	0	36
	3	0	68	0	0	32
	4	0	71	0	0	29
2	1	0	0	0	51	49
	2	0	0	0	53	47
	3	0	0	0	50	50
	4	0	0	0	50	50
3	1	47	0	0	0	53
	2	49	0	0	0	50
	3	51	0	0	0	49
	4	52	0	0	0	48
4	1	0	54	0	3	44
	2	0	49	0	1	50
	3	0	56	0	1	43
	4	0	51	0	0	49
5	1	0	81	0	0	19
	2	0	83	0	0	17
	3	0	86	0	0	14
	4	0	87	0	0	13

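### The Phase I exposure prior does not match its stated derivation: the announced 4th component is not listed, and one input is 2770 where its own source gives 3770

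*SAP*

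**What the plan says.** The Phase I dose-exposure model is log(AUC) = log(alpha) + beta·log(dose/3) + error, with AUC taken over 0-336 h in cycle 3. AUC is a Phase I co-primary variable (SAP 3.3.1). The prior for log(alpha) and log(beta) is a meta-analytic-predictive (MAP) prior built from three published studies.

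On the form of the prior, protocol 14.3.1.2 (step 3) says that three normal components approximate the MAP distribution, and then: "To allow for more robust inference in case of the discrepancy between MAP information and the trial data, a non-informative prior component was added". The SAP repeats this ("a non-informative prior component was added as the 4th component") and adds: "The respective distribution for each component and its weight is provided in Table 3-1". The tables are protocol Table 14-9 ("Prior distribution of (log(Alpha), log(Beta)) and sigma for the new trial") and SAP Table 3-1. Both show the same three rows, with weights 0.480, 0.425 and 0.095.

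On the data, protocol 14.3.1.2 (step 2) says the published results are "summarized in Table 14-8 after unit conversion is applied on source data". No other transformation is mentioned. Table 14-8 gives Study 2 at 10 mg/kg as 2770 µg·day/mL (CV 33%, n = 83). The source for that cell is Table 14-11, "Area under the pembrolizumab concentration versus time curve at steady state by treatment arm", which reports a geometric mean of 3.77 g·day/L.

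**The concern.** The text announces four components and a complete table, and the table has three. Either the sentence or the table is wrong, and the component at issue is the one meant to protect against conflict between the external data and the trial. The input figure is a second, independent mismatch, and it sits at the top dose of one of the two largest data sets, where it has most leverage on the slope.

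The prior is used in three places: the posterior AUC summaries and probability of reaching 1000 µg·day/mL (SAP 3.3.1.1.1), the predicted-AUC plot for the CSR (SAP 3.3.1.1.2), and the design simulations, where "the Bayesian Linear Regression Model was implemented using the simulated AUC data with the priors specified in Section 14.3.1.2" (protocol 14.3.1.4). As the documents stand, a reader cannot derive the prior from its stated sources or tell whether three or four components were used.

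**Working it through.** **1. Weights.** 0.480 + 0.425 + 0.095 = 1.000. Nothing is left for a 4th component.

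**2. What the three printed rows amount to.**
- log(alpha) mean: 0.480×6.40 + 0.425×6.38 + 0.095×6.42 = 6.393.
- log(alpha) variance: 0.480×0.683² + 0.425×0.403² + 0.095×1.410², plus 0.0002 between components, = 0.482; SD 0.694.
- log(beta): mean 0.050; variance 0.480×0.180² + 0.425×0.118² + 0.095×0.257² = 0.0277; SD 0.167.
- Correlation: -0.44.

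**3. Unit conversion of the sources.**
- Study 2 (×1000): 0.643 becomes 643, as in Table 14-8; 3.77 becomes 3770, not 2770.
- Study 3 (÷24): 2210, 7750 and 36,620 become 92, 323 and 1526, all as in Table 14-8.
- Study 1 is carried over unchanged.

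**4. Which Study 2 figure is right.** Table 14-11 gives a median of 3.76 and 5th-95th percentiles of 2.13-5.99. With CV 33% the log-scale SD is √log(1 + 0.33²) = 0.3215, and exp(1.645×0.3215) = 1.697. Around 3.77 the 5th-95th percentiles are 2.22-6.40; around 2.77 they are 1.63-4.70. Only 3.77 fits.

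**5. Effect on the Study 2 slope.** log(2770/643)/log(10/2) = 0.907; log(3770/643)/log(10/2) = 1.099.

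**6. Refit of the stated model.** This is an MCMC fit with the Table 14-7 hyperpriors and the protocol's likelihoods: sample mean ~ N(log(alpha) + beta·log(d/3), sigma²/n), sample variance ~ Gamma((n-1)/2, (n-1)/(2·sigma²)). Ranges are over repeated fits.

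| Quantity | Printed mixture | Refit, 2770 | Refit, 3770 |
|---|---|---|---|
| log(beta) mean | 0.050 | 0.051-0.052 | 0.128 |
| log(beta) SD | 0.167 | 0.165-0.167 | 0.138-0.141 |
| log(alpha) SD | 0.694 | 0.68-0.70 | 0.86-0.87 |
| Correlation | -0.44 | -0.45 | about -0.29 |
| P(AUC ≥ 1000 at 3 mg/kg) | about 0.185 | about 0.185 | 0.241 |

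The printed prior is the 2770 fit, so 2770 entered the calculation and is not merely a typing slip in Table 14-8. The three rows match the whole MAP, tails included (2.5%-97.5% of log(alpha): 5.00-7.81 printed, 5.00-7.79 refit). The wide third row is therefore part of the MAP approximation and not the missing non-informative component.

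**7. Effect on a posterior.** The documents give no PDR001 AUC data, so the inputs here are assumed: dose means exactly on a Table 14-13 profile, within-dose SD 0.4 (the protocol's simulation value), patients at 1/3/10 mg/kg as in the protocol's sample sets, and sigma integrated out under its printed prior.

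| Case | Patients | P(AUC > 1000), printed prior | P, 3770-based prior |
|---|---|---|---|
| Profile 1, 3 mg/kg (true AUC 1097) | 6/6/6 | 0.78 | 0.81 |
| Profile 1, 3 mg/kg | 3/12/9 | 0.83 | 0.80 |
| Profile 3, 1 mg/kg (true AUC 994) | 6/6/6 | 0.51 | 0.39 |
| Profile 3, 1 mg/kg | 3/12/9 | 0.54 | 0.39 |

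Profile 1 shifts by about 0.04 or less. Profile 3 crosses the protocol's criterion of more than 50%. In a rerun of the Table 14-14 recommendation rates, at the dose checked in each of Profiles 1, 2, 4 and 5, the rate moved by at most 4 points.

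**The case against.** Four objections carry weight.

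- **The printed mixture is a proper, usable prior.** That is so. The defect lies in one input to its derivation and in a description that does not match its table.
- **Correcting the input need not bring the estimate closer to the truth.** Also so. For Profile 1 at 10 mg/kg with 6/6/6 patients (truth 3655), the printed prior predicts 3484 (-4.7%) and the 3770-based prior 3815 (+4.4%). The case for correction is traceability.
- **The model only guides.** Protocol 6.2.3 and SAP 3.3.1 base dose decisions on safety, PK and PD data together, and escalation is closed. This limits the consequence to reporting.
- **The assumed data are not the trial's data.** The 58 escalation patients include 3 and 5 mg/kg Q4W (protocol 1.2.1.2), and the dose-determining PK set requires sufficient cycle 3 samples. For this reason the check uses only the protocol's own sets of 18 to 24 patients.

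Text extraction does not explain the missing row: the same three rows stand in both documents, and their weights close at exactly 1.

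A reader might infer that escalation was run without a robust component. The documents do not show this. They do not say which prior was run, and Table 14-14 cannot settle it: any 4th component used for comparison has to be invented, most cells barely change when one is added, and those that do change are inconclusive.

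**Conclusion.** Both mismatches hold. The robust component promised in the text is absent from the printed prior, and the printed prior rests on 2770 where the stated source gives 3770. The change in the prior is clear: log(beta) mean from 0.05 to 0.13, log(alpha) SD from 0.69 to about 0.86, prior P(AUC ≥ 1000 at 3 mg/kg) from about 0.185 to 0.24. The posterior effect is small in the Profile 1 check and material for a dose almost exactly at the threshold; both statements rest on assumed data at 1, 3 and 10 mg/kg.

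Two stronger readings should be resisted. One is that the recommended Phase II dose was affected: without PDR001 AUC data the actual shift is unknown, and the dose did not rest on this model alone. The other is that three doses' worth of data always make the prior harmless: Profile 3 shows otherwise.

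This is worth correcting because it concerns a Phase I co-primary analysis and the correction is cheap. The three source studies also use different AUC windows (0-28 days, steady state on a three-weekly schedule, 0-14 days). That is a separate limitation, which correcting 2770 does not address.

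**What to change.** 1. Issue an erratum changing the Study 2 entry at 10 mg/kg in Table 14-8 to 3770.
2. In Table 14-9 and SAP Table 3-1, state which prior was actually used. If three components, delete the sentence about the 4th. If four, print the 4th component's means, SDs, correlation and weight as used, with all weights summing to 1. Do not choose a new component now that the data are known.
3. Keep the prior actually used as the pre-specified analysis.
4. In the CSR that reports the Phase I dose-exposure analysis, add one sensitivity run, labelled as such: the posterior summaries and predicted-AUC plot with the prior re-derived from 3770.

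The cost is a correction to three tables (for the SAP, by amendment or addendum as its introduction provides), one re-derivation and rerun of an existing model, and one extra set of summaries with a plot. No new data are needed.

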3.3.1.1.2 Reports of dose-exposure relationship

A plot of predicted AUC during the interval of 0 to 336 hours after the first dose of treatment in cycle 3 with 95% CI will be produced based on the dose determining pharmacokinetic set.

3.3.1.1.3 BLRM for DLTs

In addition to the Bayesian linear model, an adaptive, 2 parameter Bayesian logistic regression model (BLRM) will be used to estimate the probability of a DLT in the first cycle of treatment. The prior distributions for the BLRM are derived based on available pre-clinical data and clinical data for Nivolumab and Pembrolizumab.

The dose-toxicity relationship in the dose escalation part of the study will be described by the following logistic regression model:

$$logit(\pi_{(d)}) = log(\alpha) + \beta log(d/d^*), \quad \alpha > 0, \beta > 0$$
 [2]

where $logit(\pi_{(d)}) = log(\pi_{(d)}/(1-\pi_{(d)}))$, and $\pi_{(d)}$ is the probability of a DLT at dose d. Doses are rescaled as d/d* with reference dose d*=3 mg/kg of PDR001. As a consequence α is equal to the odds of DLT rate at d*. Note that for a dose equal to zero, the probability of toxicity is zero.

Prior specifications

This study uses a mixture prior consisting of two components.

Table 3-2 Prior distribution of model parameters

Parameter	Means	Standard deviations	Correlation	Weight	
Component 1: weakly informative priors					
$log(\alpha)$, $log(\beta)$	-2.692, -1.26	1.0, 1.0	0	0.8	
Component 2: priors for a more toxicity sensitive population					
$log(\alpha), log(\beta)$	-2.3, 0	2, 1	0	0.2	

For further details on the BLRM model including the model structure, the prior specification for the model parameters, and examples of hypothetical decisions that may be followed during the dose escalation, refer to [CPDR001X2101 Amendment 8 Appendix 3-Section 14.3.2].

After each cohort of patients, the posterior distributions for the probabilities of DLT rates at different dose levels are obtained. The results of this analysis are summarized in terms of the probability that the true rate of DLT at each dose level lies in each of the following categories:

- [0, 16%) under-dosing
- [16%, 33%) targeted toxicity
- [33%, 100%] excessive toxicity

Dose recommendation will also be guided by the EWOC principle, which mandates the dose for the next cohort to have less than 25% chance of excessive toxicity. The final estimate of the RP2D/MTD will also satisfy this condition.

In case of changes in dosing schedule during dose-escalation, a BLRM of the same functional form described in [CPDR001X2101 Amendment 8 Appendix 3] will be used to estimate the

dose-DLT relationship for each schedule based on a newly derived prior incorporating the historical trial data and the on-study data from previous schedule. At each time the model is updated, all available information on the dose-DLT relationship from all explored dosing schedules will be used. In order to account for between schedule variability in the assessment of a given dosing schedule, the DLT data obtained from other explored dosing schedules will be down-weighted.

Change in dosing schedule

In the event of a change in dosing schedule, then a new BLRM will be set up. This new BLRM will have the same functional form as equation [2] and will incorporate down-weighted existing dose escalation data in the prior distribution (see [CPDR001X2101 Amendment 8 Section 14.3] for technical details). For comparability, the dose for the new and old model will be in mg/kg per cycle.

For a Q4W schedule, the doses of PDR001 will be rescaled (doses are multiplied by 1/2). In addition, the information from Q2W will be incorporated by down-weighting the data directly using the following weight "w": (Chen and Ibrahim 2006, Neuenschwander et al 2010):

$$w = \frac{1}{1 + \frac{2n\tau^2}{\sigma^2}} = \frac{1}{1 + \frac{2n}{n_{\infty}^*}}$$

where n is the sample size of historical data, σ is the "outcome standard deviation" for one observation and τ is the between trial standard deviation. σ is the standard deviation of all data from one historical trial which may include several dose levels. For the Q4W schedule, σ was chosen as 2 and τ was set as 0.5 to correspond to moderate between-trial variability with the Q2W schedule. Note that the weights can also be expressed as a function of n and n^*_{∞} , the maximum prior effective sample size under infinite historical information for which

$$n_{\infty}^* = \frac{\sigma^2}{\tau^2}$$

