#### Component 1:

A weakly informative bivariate normal prior for the model parameters  $(\log(\alpha), \log(\beta))$  is assumed based on prior information (medians) for the probabilities of DLT at each dose, from PDR001 preclinical data and data on Nivolumab and Pembrolizumab, and considering wide confidence intervals. The priors are obtained as follows:

- For the purposes of tuning the prior for the BLRM model, the median DLT rate at 1 mg/kg Q2W is assumed to be at 5%, and the median DLT rate at 10 mg/kg Q2W is assumed to be at 10%. For the remaining doses, median DLT rates a priori are assumed linear in the logit-scale as a function of log-dose.
- Based on the above specified medians for the DLT rate at certain dose and wide prior confidence intervals, the optimal parameters of the bivariate normal distribution can be obtained following the procedure described by (Neuenschwander et al 2008). Based on Neuenschwander's procedure, the initial set of prior  $(-2.692, -1.26, 2.484, 0.745, -0.765)$  is derived.
- The initial set of prior is then fine-tuned in combination with the component 2 prior, by adjusting the SD of  $\log(\alpha)$  and  $\log(\beta)$  as well as setting the correlation between  $\log(\alpha)$  and  $\log(\beta) = 0$ , to achieve reasonable performance for the hypothetical dose-escalation scenarios in [Section 14.3.2.3](#).
- The Component 1 is set to be  $(-2.692, -1.26, 1.0, 1.0, 0)$

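### SAP 3.3.1.1.3 gives two incompatible dose scales for the Q4W toxicity model; with d* = 3 mg/kg and the printed prior kept, the overdose probability differs up to about twofold

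*SAP*

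**What the plan says.** The toxicity model in SAP 3.3.1.1.3 is a logistic regression of the DLT probability on log(d/d*): "Doses are rescaled as d/d* with reference dose d*=3 mg/kg of PDR001". Protocol 14.3.2.2 shows that the prior was elicited per Q2W administration. For component 1, for example, "the median DLT rate at 1 mg/kg Q2W is assumed to be at 5" per cent.

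If the schedule changes, the SAP keeps the functional form of that equation and uses a model "based on a newly derived prior incorporating the historical trial data and the on-study data from previous schedule". It then fixes the unit: "For comparability, the dose for the new and old model will be in mg/kg per cycle". The next paragraph adds: "For a Q4W schedule, the doses of PDR001 will be rescaled (doses are multiplied by 1/2". Q2W data are down-weighted by a stated formula. No reference dose and no prior are printed for the new model.

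SAP 2.1.3.4 defines the cycle as 28 days for both Q2W and Q4W. The SAP points to Protocol 14.3 for technical details of the schedule change, but that appendix contains no schedule-change model. Protocol 10.4.2 leaves the down-weighting details to the analysis plan.

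**The concern.** Over 28 days, a Q2W dose of d mg/kg amounts to 2d and a Q4W dose of q mg/kg amounts to q. On the per-cycle scale nothing is halved. Multiplying q by one half belongs to another scale, on which Q2W doses stay as they are and Q4W doses become Q2W-equivalent per infusion. Either scale is coherent alone and puts a Q4W dose at half the same Q2W dose. The two sentences together are not coherent: Q2W enters as 2d and Q4W as q/2, a ratio of four.

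The position relative to d* matters too. The intercept prior describes the log-odds of a DLT at 3 mg/kg per Q2W infusion. If doses move to mg/kg per cycle and d* stays at 3, the same prior is attached to 1.5 mg/kg per Q2W infusion, which shifts every probability.

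At stake are the posterior interval probabilities that SAP 3.3.1.1.4 puts in the CSR body and the BLRM listing in its appendix. Two programmers following the text could report different values, and the literal combination understates the overdose probability.

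**Working it through.** **Inputs.** Mixture prior for (log α, log β) from SAP Table 3-2: weight 0.8 on means −2.692, −1.26 with SDs 1, 1; weight 0.2 on means −2.3, 0 with SDs 2, 1; correlations 0. Reference d* = 3 mg/kg. Overdose means a DLT rate of 33% or more, and the limit is a 25% probability. Weight for Q2W data w = 1/(1 + 2nτ²/σ²), with σ = 2 and τ = 0.5.

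**Reproducing the plan.** Integrating logit π = log α + β log(d/3) over the prior gives an overdose probability of 0.014, 0.026, 0.062 and 0.185 at 0.3, 1, 3 and 10 mg/kg. Protocol Table 14-17 prints 0.014, 0.026, 0.061 and 0.185.

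**Scales for a Q2W dose d and a Q4W dose q.**

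- Per cycle, d* = 3: 2d/3 and q/3.
- Halved, d* = 3: d/3 and (q/2)/3.
- Both sentences, d* = 3: 2d/3 and (q/2)/3.
- Per cycle, d* = 6: 2d/6 = d/3 and q/6 = (q/2)/3, identical to the halved scale.

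**Printed prior only.**

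| Q4W dose (mg/kg) | Per cycle, d* = 3 | Halved, d* = 3 | Ratio |
|---|---|---|---|
| 3 | 0.062 | 0.034 | 1.8 |
| 5 | 0.109 | 0.051 | 2.1 |
| 10 | 0.185 | 0.109 | 1.7 |
| 20 | 0.260 | 0.185 | 1.4 |

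The largest ratio between 0.5 and 40 mg/kg is 2.13, at 5 mg/kg. Per-cycle doses with d* = 6 return the halved column exactly.

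**With Q2W data.** Patient numbers per dose are not in the documents, so this uses hypothetical scenario 25 of Protocol Table 14-20: 0 of 7 with a DLT at 1 mg/kg and 1 of 5 at 3 mg/kg. With n = 12, w = 1/(1 + 2 × 12 × 0.25/4) = 1/2.5 = 0.40.

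| Q4W dose (mg/kg) | Halved | Per cycle, d* = 3 | Both sentences |
|---|---|---|---|
| 5 | 0.018 | 0.038 | 0.008 |
| 10 | 0.087 | 0.128 | 0.038 |
| 20 | 0.177 | 0.219 | 0.128 |

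The two coherent scales differ 2.1-fold at 5 mg/kg and 1.5-fold at 10 mg/kg. At 10 mg/kg, applying both sentences gives less than half the halved-scale value (0.038/0.087 = 0.44).

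**Closer to the trial.** Protocol 1.2.1.2 reports 58 patients and no DLT, at 1, 3 and 10 mg/kg Q2W and 3 and 5 mg/kg Q4W. Assuming 6/6/6 or 16/16/6 DLT-free patients at 1/3/10 mg/kg Q2W, with no Q4W data, the overdose probability at 3 and 5 mg/kg Q4W is at most 0.0034 on all three scales.

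**The case against.** The strongest reply is that the halving sentence simply carries out the comparability sentence: it puts Q4W doses on the old model's Q2W scale, and the words about mg/kg per cycle are loose. The SAP never says to double Q2W doses. That is a plausible account of the intent, but it requires setting aside the sentence that names the unit for both models. Per-cycle units for the old model do mean doubling Q2W doses.

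Second, the SAP does not say that d* stays at 3 mg/kg. It promises the same functional form and a new prior, and prints neither a new d* nor that prior. This stands. If d* moves to 6 with the per-cycle scale, the two coherent scales coincide and the gap is zero, so the twofold figure is conditional.

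Third, a reader might infer a difference of more than threefold. Between the two coherent scales the printed prior does not support that. It arises when per-cycle dosing with d* = 3 is set against both sentences combined (0.128/0.038 = 3.4 at 10 mg/kg in the illustration). Among the assumed down-weighted Q2W data sets tried, the ratio of the two coherent scales ran from 0.76 to 3.1. The top value came from one case: six DLT-free patients at 1 mg/kg only, 0.058 against 0.019 at 5 mg/kg Q4W. The documents do not give those data.

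Fourth, a reader might take the 20 mg/kg row of the prior table (0.260 against 0.185) as a changed escalation decision. It is a prior-only value, whereas the schedule-change model always includes Q2W data. With scenario 25 neither coherent scale reaches 25%. The highest provisional dose in Protocol Table 6-2 is 10 mg/kg, although levels could be added.

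**Conclusion.** The contradiction is real. SAP 3.3.1.1.3 states two dose scales for one model, and no other text settles which was used. With d* = 3 mg/kg and the printed prior, the overdose probability at a Q4W dose differs by up to about twofold between the coherent scales. Applying both sentences literally gives a fourfold instead of a twofold discount and understates that probability. These sizes assume that the Table 3-2 prior stands in for the unprinted one. The figures with data are illustrative.

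The documents do not support reading this as a threat to a dose decision. Phase I is reported complete in the Amendment 07 rationale and no DLT occurred. Under the printed prior, the highest value at a treated Q4W dose is 0.109, well below 25%. What is affected is the accuracy and reproducibility of the Q4W model results reported in the CSR.

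**What to change.** Reconcile the two sentences so that one dose unit covers both Q2W and Q4W data, and state how each schedule's doses enter the model, the matching d* and the prior actually used. Halved Q4W doses with d* = 3, and per-cycle doses with d* = 6, are algebraically the same, so either wording serves if it matches the program. Then confirm that the reported Q4W interval probabilities and listing were produced on that single scale, and re-run them if not. The cost is one or two SAP sentences and a check of existing output. No dose or escalation rule is proposed.
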